## 3.0 Investigational Plan

## 3.1 Overall Study Design

This is a Phase II study of orally administered ivosidenib in patients with advanced solid tumors (nonresectable or metastatic) or enhancing gliomas. Participants are required to have a histologically consistent diagnosis of *IDH1* gene-mutated tumor that is not eligible for curative therapy. Participants must have received appropriate standard of care treatment options {in the opinion of the treating investigator).

Each participant's course of treatment will be comprised of the following periods:

**Pre-Treatment/Screening Period: Following informed consent, all potential participants will undergo Screening procedures to determine eligibility within 28 days prior to the start of study treatment on Cycle 1, Day 1 (C1D1), with the exception of baseline radiographic scans, which should be performed within 21 days prior to C1D1. In patients with advanced solid tumors excluding brain tumors, a tumor biopsy will be collected if not done so before screening. A second biopsy will be taken at the end of the first cycle of nivolumab (approximately week 4 \pm 10 days). Additional Screening procedures are detailed in the study calendar in Section 6.1** 

Treatment Period and End of Treatment Visit: Participants who meet all study eligibility criteria will be eligible to start study treatment (criteria detailed in Section 4). Daily study treatment will begin on CIDI with planned concurrent dosing of ivosidenib and nivolumab. Cycles are 28 days (±2 days) in duration and dosing is continuous. Ivosidenib will be dosed daily on 28-day cycles and nivolumab will be infused IV every 28 days. All participants will continue to receive best supportive care according to institutional practice throughout the study, regardless of treatment arm. Study visits will be conducted every other week during Cycles 1-3 (Days 1 and 15), and Day 1 of each cycle thereafter. An end of treatment (EOT) Visit will be performed on the last day of study treatment (within 5 to 33 days of last dose of either study treatment to accommodate for potential dosing delays of up to 28 days).

Dosing		
Drug	ivosidenib	nivolumab
Dose Level 1	500 mg daily	480 mg IV q4
Dose Level -1	250 mg daily	480 mg IV q4

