**Schedule of Administration**: Ivosidenib will be administered concurrently with nivolumab beginning on CIDI to patients with an IDHI mutant solid tumor or glioma selected by CUA certified sequencing for IDHI R132 mutations. Should toxicity monitoring suggest and intolerable dose, a dose de-escalation approach will be employed according to the above dose levels. Dosing will be continuous (once daily) on a 28-day cycle. After confirmation of tolerable dose, ivosidenib will be continued throughout the rest of the trial. Nivolumab will be dosed concurrently at 480 mg IV q4 weeks starting on CIDI. After collecting baseline peripheral blood, a research biopsy will also be collected in at least the first 10 patients with advanced solid tumors - ie, not in glioma - in whom a biopsy is deemed safe by the treating physician, pending available funding. Ivosidenib will then be administered concurrently with nivolumab on a Q28 day schedule. A second biopsy will be taken at the end of the first cycle of nivolumab (approximately week 4), pending funding. Treatment with ivosidenib will continue indefinitely per treating investigator discretion.

Nivolumab will be given for up to 1 year. Either agent will be discontinued upon severe toxicity, confirmed disease progression, confirmed pregnancy, death, withdrawal of consent, or if the participant is lost to follow-up.

Radiographic assessment (CT or MRI) for evaluation of disease response will be conducted every 8 weeks (±7 days) from C1D1, independent of dose delays and/or dose interruptions, and/or at any time when progression of disease is suspected. For participants who discontinue study drugs for reasons other than disease progression or start of another anticancer agent, an assessment will be conducted at the EOT Visit. Target and non-target lesion selection and objective tumor response assessments per Response Evaluation Criteria in Solid Tumors (RECIST) vI.1and RANO criteria for glioma patients.

Participants will be assessed at every visit for AEs and concomitant medications, starting from the first dose of study treatment. Toxicity severity will be graded according to the National Cancer Institute Common Terminology Criteria for Adverse Events (NCI CTCAE) version 5.0. Additional physical exam and laboratory will be conducted at each visit as detailed in the study assessments and biomarker table.

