- Female participants with reproductive potential must have negative serum pregnancy testing within 24 h prior to the initial administration of study drug, then every 4 ± 1 week, or a negative confirmation from an obstetrician in case of equivocal serum pregnancy results. Females of reproductive potential are defined as sexually mature women who have not undergone a hysterectomy, bilateral oophorectomy, or tubal occlusion or who have not been naturally postmenopausal (ie, who have not menstruated) for at least 24 consecutive months (ie, have not had menses at any time in the preceding 24 consecutive months).
-  ctDNA to be collected C1D1, C1D15, C3D1, C4D1 (time of pt response assessment) and at time of progression. PBMCs to be collected C1D1, C1D15, C2D1, C3D1, C4D1 (time of pt response assessment) and at time of progression.

Germline DNA to be collected C1D1

Serum to be drawn C1D1, C1D15, C2D1, C3D1, C4D1 (time of pt response assessment) and at the time of progression.

Modification for 2-HG levels: Drawn on C1D1 (as baseline), at 1 month (C2D1), 3 months (C4D1) and at time of disease progression

Submit all required materials (eligibility checklist, source documentation, and signed consent form) to confirm eligibility and required pre-study procedures to the CRA a minimum of 48 h prior to the participant's scheduled therapy start date. Full details listed in Registration Procedures

Note that nivolumab will be dosed Q28 days via IV infusion, while ivosidenib will be continuous PO daily dosing

After cycle 3 (i.e., from C4 onwards), study visits will be monthly.

-  SAEs occurring within 100 days post last study drug dose must be reported to BMS World Wide Safety and Agios
-  Specific imaging modalities detailed under section 6.5 (Efficacy Assessments)
-  As clinically indicated
-  See Section 1.3.4 for research blood draw time points
-  See Section 6.4.3 Safety Laboratory Assessments

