# tumor.

The primary goal of the biopsy analysis is to determine whether the tumor has sustained an infiltration by innate and adaptive immune cells, and/or increased tumor expression of antigen expression apparatus such as components of MHC Class I, consistent with the therapeutic hypothesis. The secondary goal is to determine whether either the baseline level of inflammatory infiltrate or the level induced by ivosidenib treatment is predictive of immediate an extended response to the combination of ivosidenib with nivolumab.

The primary assays for analysis of the paired biopsies are the Nanostring 10 360 assay, an extensively validated transcript profiling assay used for semi-quantitative cell enumeration and transcriptional response in biopsies (Danaher, Warren et al. 2017), as well as immunofluorescence based direct enumeration of immune cells and their spatial co-localization. Assay is subject to change based on available technologies at the time of analysis.

The primary hypothesis for statistical analysis of the paired biopsies is to accept or reject the hypothesis that the tumor inflammation signature (TIS, or T cell-inflamed GEP), a function calculated from the abundance of 18 transcripts detected in the sample (Table below), has changed in the tumor due to therapy. This function is highly correlated with anti-PDI antibody treatment outcome (Ayers, Lunceford et al. 2017).

TIGIT	PD-LI	PSMBIO	STATI
CD27	CXCR6	IDO1	HLADRBI
CD8A	CMKLRI	CXCL9	HLAE
PD-L2	NKG7	HLADQAI	
LAG3	CCIS	CD276	

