# Table 4: Eighteen Component Transcripts of Tumor Inflamed Signature (TIS) Score

Several outcomes may be envisaged:

- Ivosidenib causes an increase in TIS in a subset of patients and that increase is associated with an increase in PFS.
- Baseline TIS is associated with PFS, and changes induced ivosidenib treatment are not associated with changes in PFS.
- Ivosidenib does not affect TIS in any patient.

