### General:

- Interruption of ivosidenib dosing for more than a total of 2 weeks (not necessarily consecutive) during Cycle 1, if due to AEs related to ivosidenib.
- Delay of starting Cycle 2 for> 2 weeks, if due to AEs related to ivosidenib.

All safety data in Cycle 1 and subsequent cycles will be monitored on an ongoing basis.

A patient who experiences a DLT at any dose level will receive appropriate treatment and supportive

care as necessary and will be monitored closely until resolution of the AE to Grade Oto 1 severity or Baseline severity, whichever is more abnormal, or until the AE is stabilized at any acceptable grade.

Patients who experience a DLT but who, in the opinion of the Investigator, are deriving clinical benefit will be permitted to continue treatment with ivosidenib at a lower dose that has been demonstrated to be well tolerated upon reasonable resolution of the DLT.

AEs will be tabulated by type, severity, and attribution. Immune responses, as assessed at baseline, post ivosidenib lead in, and week 9 (first restaging) will be analyzed by mixed effects regression for longitudinal data. Baseline and post-treatment values will also be compared between responders and non-responders.

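### The immune-response regression in Section 7.5 uses a post-lead-in time point that a concurrent-start trial does not have, and the ivosidenib-specific wording in Section 6.6.1 cannot be supported

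*Combined protocol and SAP*

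**What the plan says.** **The model.** The closing paragraph of Section 7.5 (Definition of DLT) says: "Immune responses, as assessed at baseline, post ivosidenib lead in, and week 9 (first restaging) will be analyzed by mixed effects regression". It adds a comparison of baseline and post-treatment values by responder status.

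**The dosing schedule.** Section 3.1 says "Daily study treatment will begin on CIDI with planned concurrent dosing of ivosidenib and nivolumab", then "Ivosidenib will be administered concurrently with nivolumab beginning on CIDI" and "Nivolumab will be dosed concurrently at 480 mg IV q4 weeks starting on CIDI" (CIDI is the scanned form of C1D1). Section 5.4 also starts ivosidenib on C1D1. The lead-in is mentioned nowhere outside Section 7.5.

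**The samples.** Table 3, footnote 3: "PBMCs to be collected C1D1, C1D15, C2D1, C3D1, C4D1", and again at progression; serum follows the same times. For tissue, Section 3.1 says "A second biopsy will be taken at the end of the first cycle of nivolumab", which it puts at about week 4, ±10 days. Section 1.3.4 puts the on-treatment tissue at week 5. Biopsies are planned in at least the first 10 solid-tumor patients, if funding allows.

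**The planned inferences.** Section 6.6.1 frames its primary TIS hypothesis as a change caused by therapy, with no drug named. Its secondary goal asks whether baseline infiltrate or "the level induced by ivosidenib treatment is predictive of immediate an extended response". It then lists three possible outcomes, all phrased in terms of ivosidenib; the first is "Ivosidenib causes an increase in TIS in a subset of patients and that increase is associated with an increase in PFS".

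**The concern.** A lead-in is a period on ivosidenib alone. A sample at its end would show what ivosidenib does before nivolumab is added, and Section 7.5 reads as if such a sample existed. If it does not, the model has a time point with no matching visit, and the analyst must choose a substitute after the fact. Any substitute carries both drugs, so the middle coefficient would no longer mean what its label says.

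Attribution matters because Section 6.6.1 rests the therapeutic hypothesis on ivosidenib inducing or augmenting antitumor inflammation. Section 1.6 says that PD-1 blockade itself promotes T-cell responses, so nivolumab alone is a plausible cause of a rise in TIS. Reporting a combination effect as an ivosidenib effect would misstate the mechanism carried into the later randomized studies that Section 1.2 has in view.

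**Working it through.** The documents give no power or sample-size figure for this analysis, so there is nothing to reproduce. The check sets the time points against the calendar, then asks which effects the schedule can separate.

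**Step 1: calendar.** Cycles last 28 days (Section 3.1). Study day = (cycle − 1) × 28 + day of cycle; weeks elapsed = (study day − 1) / 7.

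| Visit | Study day | Weeks elapsed | Prior exposure | Section 7.5 time point |
|---|---|---|---|---|
| C1D1 | 1 | 0 | neither drug | baseline |
| C1D15 | 15 | 2 | both | none |
| C2D1 | 29 | 4 | both | none |
| C3D1 | 57 | 8 | both | week 9 |
| C4D1 | 85 | 12 | both | none |

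Day 57 is the first day of week 9. Two of the three model time points match a scheduled draw. The post-lead-in point matches none.

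**Step 2: biopsy.** Cycle 1 ends on day 28, so the Section 3.1 window of ±10 days runs from day 18 to day 38. Week 5 in Section 1.3.4 is days 29 to 35, which lies inside that window. The two statements differ but are compatible, and both place the biopsy after both drugs.

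**Step 3: same-day order.** Section 5.7 gives nivolumab before ivosidenib on clinic days; Section 5.11 has ivosidenib taken before the infusion. These must be reconciled. Under either order both drugs start on the same day, so neither creates a lead-in.

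**Step 4: what can be estimated.** Write the mean response as μ + β_I × (ivosidenib given) + β_N × (nivolumab given), with rows (1, ivosidenib, nivolumab).

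- Blood as scheduled (C1D1, C1D15, C2D1, C3D1): (1,0,0), (1,1,1), (1,1,1), (1,1,1). The last two columns are equal, so the rank is 2 of 3 and only β_I + β_N can be estimated.
- Biopsies (baseline, about week 4): (1,0,0), (1,1,1). The rank is again 2 of 3.
- Time points as Section 7.5 words them: (1,0,0), (1,1,0), (1,1,1). The rank is 3 of 3.

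The model as worded therefore needs an ivosidenib-only sample, and the schedule has none.

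**The case against.** The strongest reply has four parts.

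**Section 6.6.1 is not wholly drug-specific.** Its one hypothesis for statistical testing speaks of therapy, and the exploratory endpoint in Section 2.2.3 refers to patients on the combination. The ivosidenib lines are envisaged scenarios, not committed conclusions. This stands. A reader might infer that the whole TIS analysis fails, but the documents do not support that: the paired biopsies can still test a change under treatment. Even the secondary goal keeps its predictive part, on-treatment level against response. Only the attribution to ivosidenib fails.

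**The model can be fitted.** A reader might infer that it cannot be run or that its middle point has no data. That too goes beyond the text. Blood at C1D15 and C2D1 and a biopsy at about week 4 lie between baseline and week 9. What is missing is a sample after ivosidenib and before nivolumab. Nor is it an error for a longitudinal model to leave out some collected visits.

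**The two matters are separate.** Section 7.5 does not mention TIS. The attribution problem comes from concurrent dosing combined with the wording of Section 6.6.1, and would remain if the lead-in sentence were deleted. This stands.

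**The consequence is limited.** The analysis is exploratory, biopsies depend on funding, and no efficacy or safety decision uses it. This also stands.

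None of it supplies the missing time point. No other section gives a model for immune data: Section 8.2.4, headed for biomarkers, contains only the DLT stopping rule. Dose holds could make actual exposure differ between drugs, but they are unplanned and tied to toxicity. Coding cumulative exposure would make the blood columns differ, but the separation would then rest on an assumed exposure-response shape.

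**Conclusion.** The point holds as a minor correction. One of the three time points in the Section 7.5 model is defined by a treatment period that the trial does not contain. The schedule can estimate only the joint effect of the two drugs, so the secondary goal and the ivosidenib-specific outcomes in Section 6.6.1 cannot be attributed to ivosidenib.

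No numerical share of a TIS change can be assigned to either drug. A reader might express this as an ivosidenib share somewhere between 0% and 100%, but that is not a valid bound: if the drugs moved TIS in opposite directions, the share could fall outside it. For the same reason, an unchanged TIS would not show that ivosidenib has no effect.

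The conclusion assumes that the C1D1 sample is drawn before the first dose, that exposure follows the plan, and that there is no concurrent comparator (the Protocol Summary compares with historical data). The primary efficacy test, the two-stage design and the broad TIS hypothesis are unaffected.

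**What to change.** 1. In Section 7.5, replace the lead-in time point with scheduled visits from Table 3: for example C1D1 as baseline, C1D15 and/or C2D1 as the early on-treatment point, and C3D1 as week 9. Section 8.2.4 is the natural place for the model.
2. Keep the progression sample out of the fixed-visit model, or summarize it separately. It exists only for patients who progress, at times set by the outcome.
3. Align the second-biopsy timing in Section 3.1 with that in Section 1.3.4.
4. In Section 6.6.1, reword the secondary goal and the envisaged outcomes as changes under the ivosidenib–nivolumab combination, in line with the primary TIS hypothesis and with no drug-specific causal claim.

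The cost is wording only: no new visit, sample or change to dosing. The mechanistic claim becomes more modest. The edit should precede analysis, so that the choice of visits is not made with the data in view.

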### 2.1.3Exploratory Objective

• To evaluate biomaterial-based biomarkers and determine their association with treatment

response.

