### 8.2 Statistical Analysis Plan

# 8.2.1 Primary Objective: Efficacy

Given that the response rate would be expected to be< 10% and PFS < 3.5 months in this patient population of IDHI mutant advanced solid tumors or gliomas, we will consider a participant to have had a positive outcome if they have a positive PFS6 (PFS6 is scored as either No or Yes) *and* they have had at least a partial response (evaluated by RANO in glioma patients and RECIST in patients with solid tumors) at the 12 week scan.

An Optimal Simon two-stage design is employed, where a probability of positive outcome less than 0.1 would not be promising and a probability of positive outcome 0.3 would warrant further interest. In the first stage, 18 participants will be accrued. If three or more participants have positive outcomes, 17 more participants will be accrued. If 7 or more out of the 35 participants have positive outcomes, the null hypothesis p<0.1 will be rejected at a=0.05. This design has 90% power if p > 0.3.

For all tumor types, six-month progression-free survival (PFS6) is defined as survival to six months after the initiation of treatment without objective tumor progression

The probability of positive outcome and 95% confidence interval will be estimated using the method of Koyama and Chen (Koyama and Chen 2008).

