# Target Lesions:

When more than 1 measurable lesion is present at baseline all lesions up to a maximum of 5 total (and a maximum of 2 lesions per organ) representative of all involved organs should be identified as target lesions and measured at baseline.

Target lesions should be selected on the basis of their size (lesions with the longest diameter), be representative of all involved organs, but in addition should be those that lend themselves to reproducible repeated measurements.

Pathological lymph nodes that are defined as measurable and identified as target lesions must have a short axis of 15 mm by CT scan. Only the short axis of these nodes contributes to the baseline sum.

A sum of the diameters (longest for non-nodal lesions, short axis for nodal lesions) for all target lesions will be calculated and reported as the baseline sum diameters. The baseline sum diameters will be used as reference to further characterize any objective tumor regression in the measurable dimension of the disease.

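### The one specified analysis linking biomarkers to tumor response splits patients into responders and non-responders, where few responders are expected; ranking the tumor change already measured would use more of the data at little cost

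*Combined protocol and SAP*

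**What the plan says.** Section 2.1.3 sets the exploratory objective: "To evaluate biomaterial-based biomarkers and determine their association with treatment" response.

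The matching analyses are scattered:

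- **Section 7.5, closing paragraph (in the DLT definition).** Immune responses over time "will be analyzed by mixed effects regression for longitudinal data"; tumor response is not named as a term in that model. The next sentence adds: "Baseline and post-treatment values will also be compared between responders and non-responders". The paragraph does not define responder.
- **Section 6.6.1.** "The primary hypothesis for statistical analysis of the paired biopsies is to accept or reject the hypothesis that the tumor inflammation signature" has changed with therapy. Among the outcomes envisaged is this one: "Ivosidenib causes an increase in TIS in a subset of patients and that increase is associated with an increase in PFS". Baseline TIS against PFS is also envisaged. No method is given for either PFS association.
- **Section 8.2.4.** The heading names biomarkers and response, but the text holds only the DLT stopping rule.

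On numbers, Section 8.2.1 begins "Given that the response rate would be expected to be< 10" percent. Section 3.1 says "a research biopsy will also be collected in at least the first 10 patients with advanced solid tumors", subject to safety and funding. Section 1.2.1 notes that most chondrosarcoma patients on ivosidenib had stable disease as best response, and that response may therefore miss the treatment effect.

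On measurement, Appendix 11.8 computes a sum of target-lesion diameters and says: "The baseline sum diameters will be used as reference to further characterize any objective tumor regression in the measurable dimension of the disease". Appendix 11.9 uses the corresponding bidimensional sum for enhancing glioma lesions.

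**The concern.** A responder split treats a patient whose lesions shrink by 25% the same as one whose lesions grow. That is tolerable when the two groups are of similar size. Here the protocol expects fewer than one patient in ten to respond and warns that disease stabilisation may be the main effect, so nearly all patients would fall in one group.

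At stake is the yield of the correlative samples for one question: do immune measures track tumor response? With zero or one responder among the biopsied patients, the comparison is either impossible or rests on a single person. The measurements behind the response category contain more information and need no further collection.

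**Working it through.** **Inputs from the documents.** Section 8.2.1: response rate below 10%; Simon design with p0 = 0.1 and p1 = 0.3, continuing with at least 3 of 18 and rejecting with at least 7 of 35. Section 3.1: at least 10 biopsied patients. The rates 0.1 and 0.3 apply to the composite outcome (at least a partial response *and* PFS6). They are used below as illustrative response rates.

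**1. Reproduce the plan's own figure.** P(reject | p) = Σ (x = 3 to 18) b(x; 18, p) · P(Bin(17, p) ≥ 7 − x).
- p = 0.1: 0.0474, within the stated 0.05.
- p = 0.3: 0.9016, matching the stated 90%.
- P(stop at 18 | 0.1) = P(Bin(18, 0.1) ≤ 2) = 0.734.

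A positive outcome requires a response, so at a 10% response rate the composite rate is at most 10%. The stopping probability is then at least 0.73.

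**2. Number of responders at a 10% rate (exact binomial, no correlation assumed).**

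| Patients | Expected | P(none) | P(at most 1) |
|---|---|---|---|
| 10 (biopsied) | 1.0 | 0.9^10 = 0.35 | 0.349 + 10 × 0.1 × 0.9^9 = 0.74 |
| 18 (stage 1) | 1.8 | 0.15 | 0.45 |
| 35 (maximum, if accrual were fixed) | 3.5 | 0.03 | 0.12 |

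At a 30% rate the problem eases: 3 expected among 10, with P(at most 1) = 0.15, and 10.5 expected among 35.

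**3. Information kept by a split.** For a normal tumor measure cut so that a fraction p respond, the large-sample efficiency relative to the uncut measure, for small correlations, is φ(z)² / [p(1 − p)].
- p = 0.1: 0.1755² / 0.09 = 0.34.
- p = 0.3: 0.3477² / 0.21 = 0.58.

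**4. Power under an assumed correlation.** The documents give no correlation between any biomarker and tumor change, so this step rests on an assumption. Biomarker and tumor change are taken as bivariate normal, with two-sided 5% tests and the 3-of-18 rule applied. Tumor change is ranked within RECIST and RANO patients, and the comparator is the responder split.

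| Response rate | Correlation | Rank correlation | Split | Difference (points) |
|---|---|---|---|---|
| 10% | 0.3 | 0.25 | 0.07 | 18 |
| 10% | 0.5 | 0.56 | 0.18 | 38 |
| 10% | 0.6 | 0.72 | 0.25 | 47 |
| 30% | 0.3 | 0.35 | 0.24 | 11 to 12 (rounding) |
| 30% | 0.5 | 0.78 | 0.57 | 21 |
| 30% | 0.6 | 0.93 | 0.78 | 15 |

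The type I error of the rank analysis is about 5–6%. In a subset of 10 at correlation 0.5, power is about 0.28 against 0.04 (10% rate) or 0.13 (30% rate), so neither method is strong there.

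The simulation has two limits. It assumes complete scans, and it does not model the worst-rank convention proposed under the fix.

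**The case against.** The strongest reply is that nothing promised is lost. The objective is exploratory, the protocol summary says relationships will be described, and no power or alpha is attached. That stands, and it is why this is an improvement and not an error.

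Three stronger readings are tempting, and the documents do not support them.

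- **That the split is the only biomarker analysis.** Section 7.5 introduces it as an addition to a mixed model, Section 6.6.1 makes change in TIS the primary biopsy hypothesis and foresees PFS associations, and Section 2.2.3 speaks of clinical outcomes generally. None of these needs responders. The split is only the sole biomarker-to-tumor-response analysis whose form is stated.
- **That a definite amount of power is lost.** Any figure depends on an assumed correlation. A calculation with 35 patients fixed also ignores the early stop: at a 10% rate and correlation 0.5, rank-correlation power is about 0.84 with 35 fixed but about 0.56 once the stopping rule is applied.
- **That response is merely a cut of percent change.** RECIST also uses non-target and new lesions, and RANO adds non-enhancing disease, steroid dose and clinical status. A patient with shrinking target lesions and a new lesion has progressed, yet would rank well on raw best percent change. Section 1.2.1 also cautions that fibrosis can confound size measurements.

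The third point shapes the fix: percent change needs a rule for such patients, and it complements the response category without replacing it.

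**Conclusion.** The point holds as an inexpensive improvement. The one biomarker-to-response analysis with a stated form uses a two-group split where the protocol expects few responders, although a continuous tumor measure is already computed.

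The scarcity of responders follows from the protocol's own expected rate: at 10%, a ten-patient biopsy subset has no responder with probability 0.35 and at most one with probability 0.74. The power gain of roughly 12 to 47 points is conditional on an assumed bivariate-normal correlation of 0.3 to 0.6, response rates of 10% or 30%, and complete scans.

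A reader might infer that the immune hypothesis would go unanswered. That goes too far: change in TIS can be tested, and its association with PFS examined, with no responders at all. Nor does a rank analysis rescue a subset of ten, where its power stays near 0.28 even at correlation 0.5.

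**What to change.** State the analysis in Section 8.2.4, for example:

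> The association of each baseline and on-treatment immune measure with tumor response will be estimated by rank correlation with the best percent change from baseline in tumor size up to progression (RECIST sum of diameters; RANO sum of products), ranked within RECIST and RANO participants separately. The worst rank is given to participants who die or progress clinically before a post-baseline scan, or whose first post-baseline assessment is progression by new or non-target lesions, or by non-enhancing or clinical RANO criteria. Immune measures will also be summarised descriptively for responders and non-responders.

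The closing sentence of Section 7.5 then moves here as the descriptive supplement. Define responder at the same time: Section 2.2.1 places response at 8 weeks, Section 8.2.1 at the 12-week scan.

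The cost is a paragraph of text, a ranking convention for patients without a usable percent change, two measurement scales handled by stratum, and slightly more analysis work. No new samples, scans or participants are needed.
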